For Aim 2, we will conduct a randomized controlled trial that will enroll patients who have to reschedule colonoscopies. We will randomly assign about 900 patients who are on the waitlist to either intervention or control arm. The intervention arm will receive a shared decision making worksheet that will cover (a) presenting pros and cons of three screening options (first available colonoscopy (wait time estimated to be ~6 months), stool-based test (with consideration that if positive, a follow-up colonoscopy may still be delayed ~3 months), and delay colonoscopy one year); (b) contact information for rescheduling their colonoscopy; and (c) contact information to connect with staff if they have questions or need more information. GI clinicians will be recruited and complete an online SDM training prior to their visit with patients who have more questions and request a GI visit. The control group will receive the standard department guidance and policies on scheduling. We will invite patients to complete a survey to track SDM, decisional conflict, overall anxiety and cancer worry, preference for colonoscopy, concerns about accessing health care-and we will also track any testing received within 6 months. We estimate sending a survey to about 700 patients across both arms and receiving 450 completed surveys.

For Aim 3, we will follow all MGH patients who had their screening or surveillance colonoscopy delayed for 12 months and will document receipt of colonoscopy or other colon cancer screening test, and if they got a colonoscopy, will calculate the wait time for colonoscopy for all of the patients on the waitlist. We will track demographic information, age, gender, race and ethnicity, primary language, zip code. We estimate that there are about 5,000 patients who have had their colonoscopy delayed that will be followed in this chart review portion of the study.

Table 1: Eligibility for patient participants

Eligible	Ineligible

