The research staff will track the number of participants screened, reason for ineligibility, the number sent invitation by mail, the number who opted out or otherwise declined participation and any reasons given for the refusal to participate. Limited information collected during the eligibility screening process will be kept for non-responders to examine non response bias.

All study staff are Collaborative Institutional Training Initiative (CITI) certified and will receive training from the PI and program manager in the study protocol. We will hold regular meetings to review screening, enrollment and completion data, to discuss protocol and standard operating procedures, and to identify and mitigate any issues that arise.

For studies involving treatment or diagnosis, provide information about standard of care at Partners (e.g., BWH, MGH) and indicate how the study procedures differ from standard care. Provide information on available alternative treatments, procedures, or methods of diagnosis.

No tests or treatments will be administered as part of this study. For Aim 2, the standard of care is that patients may call the GI scheduling group to reschedule their colonoscopy or GI schedulers may reach out to patients to reschedule a cancelled or postponed procedure. In the intervention arm, patients may still call the GI scheduling group to reschedule their colonoscopy or GI schedulers may reach out to patients. In addition, patients will receive information about their options. The materials will direct patients who are interested in colonoscopy to call the GI scheduling group. Patients who are unsure or who would like to learn about other options will be

offered the opportunity to talk with staff from Health Decision Sciences Center who will then connect patients with the participating GI clinicians to obtain stool-based tests or to discuss other concerns.

Describe how risks to subjects are minimized, for example, by using procedures which are consistent with sound research design and which do not unnecessarily expose subjects to risk or by using procedures already being performed on the subject for diagnostic or treatment purposes.

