The intervention mailings went out in four waves, about two weeks apart, between September 10, 2020 and October 22, 2020. Participants in the intervention arm received a decision worksheet in the mail followed by a call from a decision coach. A subset of participants across both arms were selected to receive a survey. Staff mailed a survey to the selected subset of control and intervention participants about 8 weeks after the intervention packet was mailed to their wave. The survey packet included a cover letter, an information sheet, an incentive (\$10 gift card), the survey and a return envelope. Patients were able to complete the survey by mail, online via REDCap, or over the phone with study staff. Staff made up to three reminder phone calls and sent a reminder mailing to non-responders with 3 additional reminder calls. Spanish-speaking research staff conducted reminder calls for Spanish-speaking participants. Staff conducted chart review to collect screening tests completed within 6 months.

Randomization and blinding: The study statistician used a computer random number generator to randomly select 800 eligible patients, assign each to intervention or control arm, and to one of 4 waves. All 800 patients were followed to track colon cancer screening tests completed and a subset in each wave were randomly selected to receive a survey to measure patient-reported outcomes. The staff who entered the data from the paper surveys and who conducted chart review to collect screening were blinded to the assignment. The statistician analyzing the results was not blinded to the assignment.

Outcomes:

Screening uptake: study staff examined medical records to determine receipt of any colorectal cancer screening test for all subjects within 6 months.

The following measures were collected in the patient survey:

SDM Process Scale: 4-item survey asks about discussion of stool test, pros and cons of colonoscopy and patient's screening preference. Total scores range from 0-4 with higher scores indicating higher shared decision making. Patients who indicated that they did not talk with anyone about CRC screening received a SDM Process score of 0.

SURE scale: the brief 4-item version of the decisional conflict scale. A point is given for each "yes" response for total scores 0-4 and we report the percentage receiving the top score of 4, which indicates no decisional conflict.

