Screening preference: One item asked patient's preferred approach to screening (with responses: colonoscopy, stool-based test, delay screening, not sure).

Additional measures were collected to describe the sample and used as covariates including whether or not the patient had a CRC discussion with health care provider in the past two months, PROMIS Scale v1.2-Global Health Physical 2a, Single Item Literacy Screener, CRC screening and history, COVID-19 worry, decision worksheet use and decision coaching exposure. Basic demographics for the full sample were collected via chart review.

Sample Size: The sample size of 800 was determined based on the screening uptake, with 800 participants, the study had 81% power to detect a difference of 10% in rates. For the survey, we assumed a 60% response rate and as a result, planned to invite about 500 patients (250 in each arm) to obtain 300 responses. With 300 survey responses, the study had 80% power to detect a difference of 0.32 standard deviation (SD) for the SDM Process score. Studies have found effect sizes ranging from 0.39SD – 0.88SD for SDM Process when comparing sites that used formal

decision support (coaching or decision aids) and those that did not. For dichotomized survey outcomes (% SURE top score and % prefer screening), with 300 responses, we had 80% power to detect a 13% difference, from 70% to 83%.

Statistical methods: Sample demographics and characteristics were compiled and compared to evaluate the balance between the two arms. Responders and non-responders to the survey were compared between arms to evaluate potential non-response bias.

The following hypotheses were evaluated using an intention to treat approach, and patients were analyzed based on their assigned arm.

1. Compared to the control group, patients in the intervention arm will be more likely to have a screening test within 6 months (the percentage of patients who had either stool test or colonoscopy in each arm compared using a Fisher Exact test). We also used cumulative incidence function to compare time to screening completion.
2. Compared to the control group, patients in intervention arm will report higher SDM scores (compared mean scores using a two sample t-test).

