3. Compared to the control group, patients in the intervention arm will (3a) be more likely to have a clear preference for colon cancer screening (either colonoscopy or stool-based test) and (3b) have less decisional conflict (i.e. higher percentage of SURE top scores). We compared the percentage of patients with these outcomes between arms using Chi-square analyses.

In a pre-specified analysis, we explored the heterogeneity of treatment effects (HTE) to identify differential treatment effects among subgroups of patients stratified by sex as a biological

variable, age, race/ethnicity, education, overall health, prior screening history, COVID worry and interaction with decision coach. We used linear or logistic regression models to test the interaction between study arms and these factors. We highlighted the subgroups that presented differential effects regardless the significance of p values for the intervention and subgroup interaction. These results are exploratory in nature as the study was not powered for any of the subgroup analyses, and there was no attempt to control for potential biases.

CONSORT:

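### The heterogeneity analysis crosses study arm with decision-coach contact, which is part of the intervention: the term is not identifiable if no control was coached, and is not a patient-subgroup effect in either case

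*SAP*

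**What the plan says.** The last part of the SAP's Statistical methods section sets out a prespecified exploration of treatment-effect heterogeneity across subgroups of patients. The listed factors include sex, age, race/ethnicity, education, overall health and prior screening history, and the list ends: "COVID worry and interaction with decision coach. We used linear or logistic regression models to test the interaction between study arms and these factors". The section adds that subgroups showing a differential effect were highlighted whatever the interaction p value. It also says that the results are exploratory, that the study was not powered for them, and that bias was not controlled.

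On who was coached:

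- SAP, Background: the strategy under test is a decision aid with telephone coaching.
- SAP, Design: "Participants in the intervention arm received a decision worksheet in the mail followed by a call from a decision coach".
- Protocol, Research Design and Methods (Aim 2): "The control group will receive the standard department guidance and policies on scheduling".
- Protocol, same section, standard-of-care answer: patients who are unsure or want to hear about other options are "offered the opportunity to talk with staff from Health Decision Sciences Center". This appears only in the description of the intervention arm.
- SAP, Outcomes: the additional measures, also used as covariates, include "COVID-19 worry, decision worksheet use and decision coaching exposure". The SAP does not say whether coaching exposure came from a call log or the survey, whether controls were asked, or how controls were coded.

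**The concern.** A subgroup analysis asks whether the effect of assignment differs between kinds of patient, so the factor must be something that assignment cannot change and that exists in both arms. Coach contact fails on both counts. It happens after randomisation, it is one of the two things the intervention arm was given, and as far as the documents show it has no counterpart in the control arm.

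Patients who take a coach's call may differ from those who do not in how likely they are to be screened anyway. A coach subgroup can then show a differential effect from selection alone and be read as evidence that coaching drives the benefit. Because the SAP highlights differential subgroups regardless of p value, such a result could be highlighted even if it were not significant.

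**Working it through.** The plan gives no figure for this analysis, so there is none to reproduce. The check has two parts: whether the term can be estimated, and what it would measure.

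**1. Identifiability**

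Let A = arm (0/1) and C = coach contact (0/1). The model described is

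E[Y] = b0 + b1·A + b2·C + b3·A·C (on the logit scale for binary outcomes).

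The interaction is b3 = (m11 − m10) − (m01 − m00), where m_ac is the mean in arm a with contact c. Estimating m01 needs coached controls.

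*Case (a): no coached controls.* C = A·C for every patient. Three cells have data and there are four coefficients, so only b2 + b3 = m11 − m10 can be estimated. The rank of [1, A, C, A·C] was computed as follows (share coached assumed):

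| Per arm | Coached, intervention | Coached, control | Rank of 4 |
|---|---|---|---|
| 400 | 240 | 0 | 3 |
| 150 | 90 | 0 | 3 |
| 400 | 240 | 1 or 20 | 4 |
| 150 | 90 | 5 | 4 |

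The rank is also 3 with about 30%, 50% or 70% of the intervention arm coached.

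*Case (b): a few coached controls.* The model fits, but the estimate rests on those few patients. With 3 coached controls and half of 400 intervention patients coached, the standard error of b3 in outcome SD units is √(1/3 + 1/397 + 1/200 + 1/200) = 0.59. With 150 per arm it is about 0.61, nearly twice the 0.32 SD that the SAP's Sample Size section gives as the detectable difference for the SDM Process score.

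**2. What selection alone can produce**

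Sample sizes are from the SAP: 800 patients randomised 1:1 (400 per arm), and for the survey "planned to invite about 500 patients (250 in each arm) to obtain 300 responses", taken as 150 per arm. All other inputs are assumptions found in neither document: zero true effect; 60% of patients reachable and all of those coached in the intervention arm; uptake 35% if reachable and 20% if not.

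- Control uptake: 0.6 × 0.35 + 0.4 × 0.20 = 0.29.
- Coached minus control: 0.35 − 0.29 = +6 points.
- Uncoached minus control: 0.20 − 0.29 = −9 points.
- False gap: 6 + 9 = 15 points.

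For 400 in the intervention arm (240 coached, 160 not), the standard error of the gap is √(0.35 × 0.65/240 + 0.20 × 0.80/160) = 0.044, so z is about 3.4. For 150 (90 and 60) it is 0.072, so z is about 2.1.

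Simulation (40,000 runs per row) of coached versus uncoached within the intervention arm gave the shares below with |z| > 1.96. Each pair is difference in proportions / logistic Wald.

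| Reached | Uptake, reachable v not | Contact known for 800 | Contact known for 300 |
|---|---|---|---|
| 60% | 35% v 20% | 92% / 91% | 55% / 50% |
| 40% | 35% v 20% | 91% / 91% | 52% / 53% |
| 80% | 35% v 20% | 80% / 75% | 45% / 31% |
| 60% | 32.5% v 27.5% | 20% / 18% | 11% / 9% |
| 60% | 35% v 25% | 59% / 57% | 28% / 24% |
| 60% | 40% v 20% | 99% / 99% | 77% / 74% |
| 60% | 27.5% v 27.5% | 5% / 5% | 5% / 5% |

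Case (b), with the first row's inputs and 5% of controls reporting contact (20 of 400, or 8 of 150):

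- If contact in controls is unrelated to uptake, the interaction averages 15 points with zero true effect. The standard error is about 11 points (800) or 18 points (300), and 27% or 14% of trials are nominally significant.
- If those controls are reachable patients (uptake 35%), the remaining controls average (0.29 − 0.05 × 0.35)/0.95 = 0.287. The expected interaction is (0.35 − 0.20) − (0.35 − 0.287) = about 9 points, nominally significant in about 13% (800) or 8-9% (300).

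**3. Related point, not quantified**

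The SAP states: "Basic demographics for the full sample were collected via chart review". COVID worry, and overall health if it is the "PROMIS Scale v1.2-Global Health Physical 2a" measure, appear to come from the survey. That was mailed about 8 weeks after the intervention packet and is available only for responders. Whether the intervention changed these measures is not documented.

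**The case against.** Four arguments can be made for the plan.

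- **Non-identifiability is conditional.** Coaching exposure is listed among the collected measures and the survey went to both arms, so controls may have been asked. One positive answer restores full rank. This stands, and it is why the point is put as two cases. It does not help in case (b), where the factor is still a treatment component.
- **The limits are disclosed.** The SAP calls the analysis exploratory, unpowered and uncontrolled for bias. That keeps the severity low. It does not supply the missing cell or turn coach contact into a patient characteristic.
- **The error rates depend on assumptions.** This stands. They run from about 5% to 99% as the uptake difference goes from 0 to 20 points. They describe the within-arm contrast left after a redundant column is dropped, and the SAP does not use a significance cut-off to choose what it highlights. The 300-responder figures also carry over full-sample inputs, although responders may be easier to reach.
- **The direction of selection is not settled.** The Protocol sends patients who want colonoscopy to scheduling and unsure patients to the decision-center staff, which could reverse the bias. The SAP describes a call to intervention participants. Bias in either direction would still be selection and not effect modification.

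**Conclusion.** The concern holds, as a minor point. With no coached controls, the stated interaction is not identifiable (rank 3 of 4), and this needs no numerical assumption. With some coached controls it can be computed, but it contrasts post-randomisation groups that are not comparable between arms. Which case applies cannot be told from the documents, because the coding of coach contact in controls is not given.

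The 15-point false gap and its rates show how large a selection artefact could be under assumed inputs. They are not estimates for this trial. The comparisons of screening uptake, SDM score, screening preference and SURE score by assigned arm are unaffected.

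**What to change.** 1. Remove coach contact from the arm-by-factor interaction models and record the departure: it was on the prespecified list, and is not tested as an interaction with arm because coaching was part of the intervention.
2. Describe outcomes by coach contact within the intervention arm only, labelled as a non-randomised comparison.
3. State where the coach-contact data came from (call log or survey), how many patients have it, and how controls were coded.
4. Label modifiers taken from the survey as measured after the intervention and available for responders only.
5. For every remaining prespecified factor, report the interaction estimate with its 95% confidence interval alongside any highlighted subgroup.

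The cost is a few sentences in the SAP, one exploratory model per outcome replaced by a descriptive table, and a note of the change. No new data are needed and the main comparisons do not change.
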